14.0 Informed Consent

All subjects and their parents or caregivers for this study will be provided a University of Minnesota IRB-approved consent form describing this study and providing sufficient information for subjects to make an informed decision about their participation in this study. The consent form will be submitted with the protocol for review and approval by the University of Minnesota IRB for the study. The formal consent of a subject, using the IRB-approved consent form, must be obtained before that subject is submitted to any study procedure. This consent form must be signed by the subject or legally acceptable surrogate, and the investigator-designated research professional obtaining the consent. A blank copy of the IRB-approved form must be kept on-site and by the sponsor-investigator.

15.0 Laboratory Testing Procedures

All labs will be sent to Fairview Labs for in-house processing, or to be forwarded by Fairview Labs to outside processing facilities:

Fairview Diagnostic Laboratories
[name]
[name]
[name]
[contact] voice, [contact] fax

15.1 Other parameters being monitored. The following parameters will be monitored at baseline and then every 3 months for the first year of treatment, and then every 6 months thereafter: subject weight, height, occipital-frontal circumference, comprehensive metabolic panel (including serum creatinine and estimated GFR and liver function tests), CBC with platelets and differential, lipid panel, neurologic exam to assess for peripheral neuropathy, and urine pregnancy test in all post-pubertal females. It is acceptable for this interval safety monitoring to not occur at the primary study site as long as the neurologic exam could be performed by an experienced practitioner.

16.0 Subject Withdrawal

16.1 How to withdraw subjects. Patients can choose to withdraw from the study at any time. We will request that the patients notify the investigators if they wish to withdraw from the study. Subjects will stop the study if:

- 1) The subject voluntarily chooses to withdraw from the study.
- 2) The study investigator(s) may choose to discontinue patient from study if patient is experiencing adverse effects that cannot be managed by dose adjustments of the study agent.

16.2 Data collection and follow-up for withdrawn subjects. Patients will continue to receive full clinical services in our lysosomal disease treatment clinic.

16.3 Subject compensation. There will be no compensation to subjects for participation in this clinical trial.

17.0 Study Timetable / Schedule of Events

BL = Baseline, Wk = Week, M = Month, Y = Year

Study Events	Pre-Study	BL	Wk 1	Wk 2	Wk 3	M 1, Wk 4	M 3	M 6	M 9	Y 1 M 12	M 18	Y 2-5 Annual Visits	Y 2-5 Half-Year Time-Point	Every 3 M Throughout this Research Study	Monthly Assessment after the First Year of Study Participation
Determination of leukocyte hexosaminidase activity level for GM ₂ gangliosidosis patients, or β-galactosidase activity level for GM ₁ gangliosidosis patients	X														
Informed Consent		X													
Demographics data collection		X													
Retrospective data collection		X													
Telephone follow-up call: In addition to the timetable shown here, a member of the study staff will contact the parent at least once weekly during the time when the subject is transitioning onto the ketogenic diet, and while the subject is titrating the miglustat dose, and any time the dose is decreased due to adverse events, until symptoms have re-solved. Additionally, while the subject is on a stable (goal) miglustat dose, side effects will be assessed by telephone contact or at clinic visits every 3 months throughout the study period.		X	X	X	X	X	X	X	X	X	X	X	X	X	
Miglustat goal dose = 100 mg 3X daily. Evaluation of dose titration and tolerance of miglustat therapy by tele-phone contact and during clinic visit. After 1 st year, assessments will continue for a minimum of once monthly.			X	X	X	X	X	X	X	X	X	X	X		X
Ketogenic Diet 4:1 Evaluation by ketogenic dietician and neurologist trained in ketogenic diet (a "ketogenic diet team") per institution's clinical program protocol, either at the research site or locally in subject's geographic area. After 1 st year, assessments will continue for a minimum of once monthly.		X	X	X	X	X	X	X	X	X	X	X	X		X
Neuropsychological Testing changes in neuropsychiatric status as assessed by: age-equivalent scores of Bayley Scales of Infant and Toddler Development; and of Vineland Adaptive Behavior Scales		X								X		X			
Neurological evaluation of changes in seizure frequency and severity, and of movement disorders		X								X		X			
Measurement of subject weight, height, occipital-frontal circumference, comprehensive metabolic panel (including serum creatinine, estimated GFR, and liver function tests), CBC with plate-lets and differential, lipid panel, neurologic exam to assess for peripheral neuropathy, and urine pregnancy test in all post-pubertal females. It is accept-able for this interval safety monitoring to not occur at the primary study site as long as the neurologic exam is performed by an experienced practitioner.		X					X	X	X	X	X	X	X		

Whenever possible, the scheduled assessments/exams will be conducted on all subjects for the duration of the study. However, due to disease progression or concurrent illness, some patients after enrollment may not be able to fulfill the annual visit requirement. If this occurs, a failure to appear for any given annual visit will not make any subject ineligible to continue as a research participant. For research purposes, the rarity of the gangliosidoses dictates that as much data as possible be collected on any given subject.

When any newly-enrolled subject is already using the Syner-G regimen at time of enrollment, for clinical management, the Schedule of Events for that subject will begin with the scheduled time-point that corresponds to the number of weeks or months that subject has been using Syner-G.

18.0 Data Analysis

18.1 Subject populations for analysis:

- Intention-to-treat Population (ITT): All subjects who initiate any portion of the treatment regimen in association with this study
- Per-protocol Population (PP): Includes all subjects who initiate treatment and are compliant with at least 75% of prescribed drug doses of miglustat, and at least 3:1 ketogenic diet.
- Safety population: All subjects who receive any amount of the combination treatment regimen. Due to the nature of a combination treatment, multiple groups may be identified, should partial adherence be observed.

18.2 Sample size determination. The sample size for the study was determined primarily by feasibility due to the extremely rare nature of the disease. There are two distinct sub-types to be evaluated: infantile and juvenile. Analysis will be based on variability estimates from published natural history studies^{8,11,19} of the infantile form and juvenile form, and correlation between baseline and annual follow-up for up to 4 years.

18.3 Statistical analysis. Descriptive analyses of baseline characteristics and outcomes will include means, standard deviations, medians, and ranges for continuous variables and frequencies for categorical variables. Treatment compliance for each group will also be evaluated. All analyses will be conducted separately for the two disease sub-types – infantile and juvenile – due to the highly heterogeneous patient groups.

The primary analysis for Syner-G treatment regimen will use the intention-to-treat (ITT) population and evaluate overall survival. This will be evaluated based on chronological age at time of death or conclusion of study (whichever occurs first), and compared to available natural history data. Median survival will be compared to previously reported natural history studies of infantile⁹ and juvenile¹¹ forms. Infantile median survival was estimated at 47 months based on data from the National Tay-Sachs and Allied Diseases database for patients born after 2000.⁹ Median survival for the juvenile form was estimated at 14.5 years.¹¹

A secondary endpoint will be the rate of change (i.e., slope) in neurocognitive functioning over the duration of follow-up, compared to available natural history data. This analysis will be conducted separately for each of the two sub-types: infantile and juvenile. The primary

neurocognitive functioning endpoint for both pediatric groups is age-equivalent scores of the Bayley Scales of Infant and Toddler Development for expressive communication, receptive communication, fine motor skills and gross motor skills. Another primary neurocognitive functioning endpoint for both pediatric groups is age-equivalent scores of the Vineland Adaptive Behavior Scales. Using general estimating equations (GEE) and an exchangeable working correlation structure, variance estimation for confidence intervals and P-values will take into account the possible correlated nature of multiple measurements on the same individual. Supportive analyses will include evaluation using the per-protocol (PP) population.

Safety analyses will be primarily descriptive, reporting the number and percentage of AEs and descriptive summaries. These analyses will use multiple safety populations according to which components of the combination therapy subjects were exposed to. Due to the longitudinal nature of the study and potential for later-emerging effects, the safety profile will be characterized for each sub-type over time. Supportive analyses will include evaluation using the PP population.

Subgroup analyses: analyses will be repeated among GM1 gangliosidosis patients and among GM2 gangliosidosis patients, and among the infantile and juvenile forms of both GM1 and GM2 gangliosidosis.

18.4 Missing data. Despite best efforts to avoid missing data, it is possible that some will occur and will be a potential limitation to the interpretation and generalizability of results. In particular, missing data may arise for non-survival outcomes (e.g. neurocognitive function data) in the event of death. For these instances, it is unclear whether a complete-case analysis (i.e. excluding patients who die) would be unbiased, and therefore would be unsatisfactory. It is also unclear what would be an appropriate magnitude of discount to satisfactorily represent the negative outcome of death. By conducting both the complete-case analysis (unbiased if death is independent of the non-survival outcome) and an analysis with an imputed value for instances of death (intention-to-treat type of analysis), the potential magnitude of treatment effect will be better characterized.

Missing data may also arise from “lost to follow-up.” The last-observation-carried-forward imputation will be used to satisfy this type of missing data. Sensitivity analyses to evaluate the extent to which results are dependent on the approach to missing data will be conducted, wherein multiple imputations will also be considered.

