13.2 Study population. Study population will be any patient with an infantile or late-infantile/juvenile gangliosidosis disease.

13.3 Sample size. A total of 30 infants or children:

- 5 patients with infantile Tay-Sachs disease
- 5 patients with juvenile Tay-Sachs disease
- 5 patients with infantile Sandhoff disease
- 5 patients with juvenile Sandhoff disease
- 5 patients with infantile GM1 gangliosidosis
- 5 patients with juvenile GM1 gangliosidosis

13.4 Subject recruitment. Subjects will be recruited from the investigators' clinical practice and through the Lysosomal Disease Network. This clinical trial will be posted on ClinicalTrials.gov and this may serve to recruit patients to the study.

13.5 Subject screening. Eligibility will be assessed during a baseline evaluation and will include confirmation of gangliosidosis disease via mutation analysis and tissue (e.g. leukocyte) ascertainment of level of hexosaminidase or β -galactosidase enzyme activity.

13.6 Prior and concomitant therapy. Subjects may have had previous therapies for gangliosidosis. If subjects are taking miglustat and/or pyrimethamine, and/or are on a ketogenic diet at the time of screening, they will be allowed to continue these therapies and will be allowed to participate in the Syner-G study.

13.7 Inclusion criteria. Subjects will be eligible to participate in the study if all of the following criteria are met: 1) confirmed diagnosis of infantile or juvenile GM1 or GM2 gangliosidosis via mutation analysis and tissue enzyme activity analysis (e.g. leukocyte activity of β -hexosaminidase A, including percent activity contributed from both α -subunit and β -subunits) or tissue β -galactosidase enzyme activity; 2) subjects must be age 0 - 17 years at time of enrollment; and 3) subjects and their caregivers must work closely with their University of Minnesota ketogenic diet team, and with their local ketogenic diet team, which must include a ketogenic dietician and a neurologist trained in the ketogenic diet.

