24.0 Human Subjects

24.1 GCP statement. This clinical trial will be conducted in accordance with the ethical principles that have their origin in the Declaration of Helsinki, and that are consistent with Good Clinical Practice and all applicable regulatory requirements.

24.2 Risks. The potential risks of this study are:

By participating in this study the subjects will run a slight risk of loss of privacy. The research team will make every effort to protect the subjects by making all of the data that the research team will take from the subjects' records anonymous by identifying it only with a number. Researchers will remove information such as name, address, and phone number, and replace that information with a code number. Only the research investigators will be able to identify which data belong to a given subject; thus the risk is minimal.

None of the neuropsychological tests are in any way harmful for participants, although they may be fatiguing. No embarrassing questions or sensitive stimuli will be used in the neuropsychological testing.

24.3 Benefits. Studies of miglustat in infantile, juvenile and adult gangliosidoses have demonstrated safety, but do not show significant clinical improvement.²³⁻²⁵ At the University of Minnesota, neuropsychiatric evaluations have shown improvement in some assessed domains for gangliosidosis patients using the goal miglustat dose and the ketogenic diet. Seizure frequency and severity have improved in all the patients; preliminary results suggest further improvement may be possible with the combination of miglustat and the ketogenic diet.

The ketogenic diet may provide benefits for patients with gangliosidoses by the following mechanisms:

- 1) Minimize or reduce the severity of food-drug interactions between miglustat and carbohydrates

- 2) Reduce seizure activity
- 3) Increase the bioavailability of miglustat to the central nervous system.

24.4 Recruitment. Patient recruitment is limited by availability of such patients. All individuals with these disorders will be considered. Disorders may be unevenly prevalent in Ashkenazi Jews, French Canadians, Louisiana Cajuns, and certain old-order Amish. All ethnic and racial groups will be recruited.

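### Section 18.1, read literally, leaves children already on both miglustat and the ketogenic diet out of the primary ITT set, although 13.6 and 17.0 enrol them; their membership and entry time need stating

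*Combined protocol and SAP*

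**What the plan says.** Section 18.1 gives the ITT set as "All subjects who initiate any portion of the treatment regimen in association with this study", and 18.3 makes it the primary set: "The primary analysis for Syner-G treatment regimen will use the intention-to-treat (ITT) population and evaluate overall survival". The outcome is age at death, or at study end for survivors, compared with published medians of 47 months (infantile) and 14.5 years (juvenile).

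Two other sections deal with children treated before they join. Section 13.6 concerns those who, when screened, already use miglustat, pyrimethamine or the diet, alone or in any combination, and it rules that "they will be allowed to continue these therapies and will be allowed to participate in the Syner-G study". Section 17.0 goes further and foresees a child on the whole regimen: "When any newly-enrolled subject is already using the Syner-G regimen at time of enrollment, for clinical management". That child's schedule is to "begin with the scheduled time-point that corresponds to the number of weeks or months that subject has been using Syner-G".

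The other two analysis sets in 18.1 are worded differently. Per-protocol "Includes all subjects who initiate treatment and are compliant with at least 75% of prescribed drug doses of miglustat" and on at least a 3:1 diet; it does not tie initiation to the study. The safety set rests on receiving treatment, not on starting it. Section 21.2 puts data gathered before a participant's discontinuation into the primary analysis unless consent is withdrawn, and does not carve out prior users.

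**The concern.** The primary set depends on an act, starting treatment under the study, that some enrolled children cannot perform because they have already done it. The plan does not say whether they count. In an open-label single-arm trial with 15 children per sub-type, that choice could be made after outcomes are known, and it could move the primary result.

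Either choice has a cost. Leaving these children out shrinks an already small set. Putting them in under the stated analysis counts all the time from birth to enrolment, during which they could not have died and still been enrolled. Every enrolled child shares that problem. Prior users carry an additional selection: those who died on the regimen, or gave it up, before enrolment are not there to be counted.

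**Working it through.** **The plan's own figure.** Section 13.3 lists six disease-by-onset groups of 5: 6 × 5 = 30, or 3 × 5 = 15 per sub-type. This reproduces. The synopsis equates sample size with the number enrolled, so prior users count toward the 30. Section 18.2 bases the number on feasibility; no alpha, power or effect size is given.

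**Membership, case by case, on the literal wording of 18.1.**

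| Status at enrolment | ITT | Per-protocol | Safety |
|---|---|---|---|
| On neither component, starts under the study | In | In if compliant | In |
| On one component, starts the other under the study | In (any portion suffices) | In if compliant | In |
| On pyrimethamine only, starts Syner-G under the study | In (pyrimethamine is not part of Syner-G) | In if compliant | In |
| On both components, continues | Out | Can be in | In |

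Only the last row is in question. In that row the supportive set can contain a child whom the primary set does not, so per-protocol need not be a subset of ITT.

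**Cost of leaving them out.** The documents do not give the number on both components, so no loss can be computed. For scale only, assume a one-sided 0.025 sign test within a sub-type, with probability 0.5 of outliving the natural-history median under the null and 0.8 under the alternative. With 15 children the rule needs 12 or more (exact alpha 0.018, power 0.65). With 10 it needs 9 or more (alpha 0.011, power 0.38). The plan specifies no such test.

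**Cost of putting them in without handling entry age.** Take the infantile median M = 47 months from 18.3 and assume a Weibull age at death with shape k and no treatment effect. For a child alive at entry age e:

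- median age at death = (e^k + M^k)^(1/k)
- probability of outliving M = 0.5^(1 − (e/M)^k)

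| Entry age (assumed) | k = 1 | k = 2 | k = 3 | k = 4 |
|---|---|---|---|---|
| 24 months: median | 71.0 | 52.8 | 49.0 | 47.8 |
| 24 months: P(outlive 47) | 0.712 | 0.599 | 0.548 | 0.524 |
| 36 months: median | 83.0 | 59.2 | 53.2 | 50.6 |
| 36 months: P(outlive 47) | 0.850 | 0.751 | 0.683 | 0.635 |

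Two examples: k = 1, e = 24 gives 24 + 47 = 71.0; k = 4, e = 36 gives (1,679,616 + 4,879,681)^(1/4) = 50.6. With no benefit at all, a later entrant is expected to exceed the 47-month benchmark. The calculation applies equally to new initiators and prior users of the same entry age. It does not include the further selection of prior users, for which the documents give nothing to calculate from.

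**The case against.** The best defence is that the phrase linking initiation to the study is undefined and can be read to cover treatment continued under it. Other parts of the plan lean toward inclusion: the synopsis speaks of participant survival and of retrospective as well as prospective data, 17.0 wants as much data as possible on each child, and 21.2 has no exception for prior users. An analysis set narrower than the enrolled set is not in itself inconsistent with the eligibility rules. Since the sample size rests on feasibility, no stated power is lost.

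All of that stands. A reader might infer that 18.1 and the enrolment rules flatly conflict, or that prior users are barred from the primary analysis. The documents support neither: no section states an exclusion, and the gap appears only on a literal reading. Nor does it reach everyone covered by 13.6, as the case-by-case table shows.

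A reader might also take 24.3, which says that at the site "neuropsychiatric evaluations have shown improvement in some assessed domains for gangliosidosis patients using the goal miglustat dose and the ketogenic diet", to mean that these patients prompted the trial and then entered it. Section 24.3 says neither, and it reports neuropsychiatric and seizure findings, not survival. The rationale in 5.1.1, 8.0 and 8.1 is the mouse combination study and the lack of clear benefit from miglustat alone. What 24.3 shows, together with recruitment from the investigators' own practice in 13.4, is that prior users of both components existed and could be enrolled.

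Finally, being alive at entry is not peculiar to prior users. The delayed-entry bias would remain if 18.1 were perfectly worded.

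The defence does not remove the need for a rule. Passages that lean toward inclusion do not define the set, and the literal definition points the other way.

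**Conclusion.** The point holds as a gap in the definition of the primary set. On its literal wording, 18.1 omits children already on both components at enrolment, whom 13.6 and 17.0 admit, and it lets them be in per-protocol without being in ITT. How many are affected cannot be determined from the documents.

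What is at stake in the survival result is illustrated, not estimated. With no treatment effect, entry at 24 months lifts the 47-month median by 0.8 to 24.0 months (47.8 − 47 to 71.0 − 47), and entry at 36 months by 3.6 to 36.0 months (50.6 − 47 to 83.0 − 47). These ranges rest on assumed entry ages and Weibull shapes 1 to 4, and depend heavily on shape. They describe the whole cohort. Once entry age is handled, the documents do not establish how far, or in which direction, including prior users would move the result. Selection for having survived and stayed on the regimen is a reason to look at them separately. The point should be settled before the analysis.

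**What to change.** 1. Reword 18.1 so that ITT is all enrolled children who start, or are already receiving, any component of the regimen under the study. Define per-protocol as the ITT children who also meet the compliance conditions, so that it is a subset.
2. In the primary survival analysis, keep age as the time scale but enter each child into the risk set at age at enrolment, or at first study treatment if later (left truncation). Prior users then enter at enrolment, and their earlier time on the regimen is not counted. For new initiators, the gap between enrolment and first treatment is not counted either.
3. Pre-specify a sensitivity analysis in children who start the regimen after enrolment, and say where a child on one component at entry belongs. This is needed because left truncation does not remove the selection of prior users for having stayed on treatment.
4. Report, by sub-type, how many children were on neither, one or both components at enrolment.

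The cost is SAP wording and one extra analysis, with no change to treatment or visits. The sensitivity analysis will be less precise. Delayed entry will give a less favourable and less precise median, because risk sets at the youngest ages may hold very few children; the number at risk by age should be shown beside the curve.
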